UNAIDS set targets of 90% diagnosed, 90% started on ART, and 90% virally suppressed to guide progress towards universal test-and-treat.²⁸ Yet, our work - and that of others - has shown many PLWH present late for care,^{29–31} many eligible people do not start ART, 32-36 and many who initiate do not stay on therapy. 37 The 2017 HSRC household survey found 85% of PLWH knew their status; of which 71% were on ART; and of which 88% were virally suppressed, implying just 52% of PLWH are virally suppressed. In a recent study of patient records at two clinics in Johannesburg led by [name], we found that under 50% of patients diagnosed in the test-and-treat era returned for their monthly drug pick-ups (Fig 1). In a systematic review of reasons for ART refusal led by [name], 38 we found that many PLWH who did not start ART reported they did not yet feel sick and perceived little benefit from ART. Indeed, although START³⁹ and TEMPRANO⁴⁰ showed that early ART has clinical benefits, magnitudes were relatively modest. For a patient with CD4>500, it would take 60 person-years (PY) of ART to avert one serious but non-fatal adverse health outcome. 40,41 In our review of ART refusal, other PLWH cited risks associated with social isolation, stigma, side effects, and costs of care-seeking. 42-46 PLWH face real costs to life-long daily therapy. Yet many are unaware that virally-suppressive ART eliminates sexual transmission.

4.1.3. Knowledge of the prevention benefits of ART is limited.

In a recent survey of young adults in rural South Africa ([name] K01), we found major gaps in knowledge about HIV treatment-as-prevention (TasP). Using innovative methods to elicit quantitative beliefs, 47,48 we asked respondents about the chances of HIV transmission if a serodiscordant couple had weekly sex for a year without a condom, with a condom, and without a condom but with virally suppressive ART. Respondents overestimated risk of transmission on ART (Fig, Aims), reporting annual transmission probabilities of 75% on average. The objective transmission risk is about 1%. Participants vastly underestimated the efficacy of TasP (Fig 2), even as they had accurate beliefs about condoms. We found nearly identical results in a sample of 363 Gauteng university students: respondents perceived ART to reduce infection risk by 17%; in fact, the efficacy of TasP is >95%. Qualitative studies in South Africa have also found low familiarity with TasP.49

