5.2.1.1 Protocol Changes Occurring During the Study (text added 7/30/2025)

Our original protocol specified that after conducting the RCT (Arm A vs. Arm B), we would conduct a non-randomized clinic-level demonstration project (Arm C) with the App videos shown in clinic waiting rooms. In a protocol deviation, the first 55 participants enrolled in Arms A and B received counseling on HIV TasP/U=U from one of our enumerators during the recruitment phase and coaching on the post-test knowledge questions, regardless of study arm. This data collection error means that both intervention and control participants (Arms A and B) would have received some exposure to HIV TasP/U=U content, attenuating any impact of the intervention. It also means that our analyses of the post-test knowledge and attitudes questions must omit these 55 participants. After recognizing this error, study staff were retrained and recruitment was separated into wave 1 (n=55) and wave 2 (n=80). Following the above protocol deviation, to improve power for our primary comparison, Arm C was dropped and the planned (n=45) participants were distributed to intervention (Arm B) and control (Arm A). Our main analyses include all 135 participants in Arms A and B; in sensitivity analyses we restrict the data to Wave 2 when there was no contamination of the control group.

Our original protocol specified a six-month follow-up survey that would assess changes in patient knowledge, attitudes, and mental health over time. Due to COVID-19 related delays, we were unable to conduct the six-month follow-up survey; hence, we report only on immediate post-test knowledge and attitudes and on clinical outcomes through 10 months, extracted from patient charts. All pre-specified outcomes relying on six-month follow-up surveys were not collected and are not reported on.

Our original protocol specified "VL<50 copies/ml at 6-10 months" as the primary outcome. During the study, a change in national guidelines shifted the timing of the first VL from 6 months to 3 months after ART initiation, leading us to expand our window of observation to 3-10 months. For our primary outcome, we raised the threshold for viral suppression from VL<50 to VL<200 copies/ml, because many patients do not reach VL<50 within 3 months even if they adhere to ART and to be consistent with WHO quidelines specifying <200 copies/ml as indicating zero transmission risk. We additionally report on <50 and <1000 VL thresholds.

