Our original protocol specified several clinic visit adherence and retention measures that could not be estimated due to unforeseen limitations. Due to missing dates of next appointments in patient charts and variability in 1-month and 2-month prescribing, we were unable to compute "days late for next appointment" or "days without medication", concepts that underpinned two of our three pre-specified retention measures. In lieu of these measures, we defined new, simplified measures to capture longer-run retention concepts. These measures – any ART refills after 30 days; any ART refills during months 1-2, ...months 3-4, and ...months 5-6 – are robust to 1- and 2-month prescribing, and do not rely on accurate recording of future appointment dates.

These changes are indicated in the relevant places below in this protocol and are reflected in the current record at ClinicalTrials.gov (NCT04504357).

5.2.2. Study population and recruitment.

The study population will include adult men and women (18 years and older) receiving routine HIV counseling services at three public sector clinics in Gauteng, South Africa during the study period. Under current standard of care, HIV counseling is provided at two points in time: after an HIV diagnosis (post-test counseling) and after an elevated viral load (adherence counseling). The same counselors provide both services and the study will recruit from both populations, with at least 1/3 from each group. After their visit to the HIV counselor, patients will be referred to study staff for recruitment into the study. Study staff will explain the study, assure the patient that participation is voluntary, and obtain written consent if the patient wishes to enroll. Across the two study phases, we anticipate recruiting a total of n=135 adult men and women receiving HIV counseling services at three public sector clinics in Gauteng, South Africa. (This sample size is feasible – in a prior study we enrolled 600 newly diagnosed PLWH at four clinics in six months.)

Participants who enroll in the study will participate in surveys at enrolment and at 6-months follow-up. The baseline session, including consent (5 min), intake survey (10 min), intervention (if Arm B) (15min), and immediate post-test survey (25 min), is expected to take 45-60 minutes.

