5.2.3.1 Intervention assignment, period 1 (two study arms, n=45/arm)

Arm A vs. Arm B. During the first period of recruitment, patients completing HIV post-test or adherence counseling will be referred to study staff for recruitment (Fig 7). Patients will complete a brief intake survey. They will then be randomized 1:1 at the individual level to "no exposure" (Arm A, n=45) vs. "controlled exposure to the tablet-based video intervention" (Arm B, n=45). Arm B will then receive the intervention on tablet, delivered in the study interview setting. Respondents in Arms A and B will then complete additional questions, constituting the immediate post-test survey. Comparisons of outcomes in Arm A and Arm B will enable rigorous inferences on the effect of "controlled exposure" due to randomization.

5.2.3.2 Intervention assignment, period 2 (third study arm, n-45):

Arm C "clinical exposure". We will conduct a demonstration project to assess the feasibility and acceptability of delivering the U=U video intervention in real world clinical settings, rather than in a controlled study context. After period one enrolment has been completed at the three clinics, the intervention will be integrated into routine counseling procedures at each clinic. In collaboration with clinic leadership, HIV counselors will be trained to use the tablet-based U=U intervention to enhance TasP literacy as part of routine counseling and will be provided a tablet for the duration of the pilot. Additionally, the full video intervention will be shown on TVs in the clinic waiting rooms (on repeat, in rotation with other material). All patients receiving counseling at the study clinics after a specified implementation date will be considered "exposed" to the intervention. Patients completing counseling during this period will be referred to study staff for recruitment. Patients who provide consent (Arm C, n=45) will participate in the intake and immediate post test surveys (Fig 7). Comparisons of Arm A and Arm C will enable inferences on the effect of "clinical exposure" to the intervention in a non-randomized pre/post design, comparing patients receiving counseling before and after the intervention at the same facility.

Implementation note: Arm C participants were reallocated to Arms A and B.

5.2.3.4 Text-message reinforcement.

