Women and men may engage with the issues surrounding U=U in different ways. We will recruit both men and women to the pilot study. We will assess for gender-specific barriers and facilitators in our qualitative data collection, and we will assess intervention impacts separately by gender. We note that due to the small sample size of this pilot, our primary analyses will pool men and women.

5.2.8. Power.

Our pilot study is powered to detect clinically significant impacts on U=U knowledge and attitudes. In preliminary data, we found that Gauteng university students (n=363) perceived virally-suppressive ART reduced transmission risk by an average of 20% (s.d. 25%). (The actual reduction in risk is at least 96%.) A successful intervention would substantially increase perceived efficacy of ART in reducing transmission. With 45 control participants and 45 treated participants per arm, we are powered at 97% to detect at least a 2-fold increase in perceived efficacy of TasP, from 20% to 40%. This pilot is not powered for impact on behaviors.

5.2.9. Scientific rigor of the approach to Aim 2.

Aim 2 will establish feasibility and acceptability of delivering U=U information via video in "controlled" and "clinical" settings, and will assess effects on knowledge, attitudes, and preliminary impact on ART adherence in a pilot trial. The approach is scientifically rigorous because:

- a) We will evaluate the "controlled exposure" intervention in a randomized trial, ensuring high internal validity.
- b) We will assess feasibility and acceptability of clinic-level integration of the intervention into routine HIV counseling, the delivery modality most likely to be scaled up and the approach to be tested in a future R01.
- c) We will evaluate impact with respect to theory-driven, validated measures of intervention acceptability, TasP knowledge and attitudes, HIV prevention altruism, and internalized stigma, which we will pre-test in Aim 1.
- e) We will establish feasibility of collecting data on behavioral impact through linkage to patient charts.
- f) The study is appropriately powered for a pilot trial that will establish convincing evidence of intervention acceptability and preliminary impact, which can be further tested in a larger scale trial in a future R01.

6. Data management and storage

Data with patient identifiers (i.e. names, addresses) will be stored at HE²RO on a password-protected server, as described below.

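### Section 5.2.8 still claims 97% power at 45 per arm for the knowledge outcome, but 5.2.1.1 leaves only 80 participants in that analysis (about 94%), and the baseline appears as both 17% and 20%

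*Combined protocol and SAP*

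**What the plan says.** Section 5.2.8 gives the only power statement in the documents, for the outcome group the pilot says it is powered for (knowledge and attitudes): "With 45 control participants and 45 treated participants per arm, we are powered at 97" per cent, "to detect at least a 2-fold increase in perceived efficacy of TasP, from 20% to 40" per cent. The same section says the pilot is not powered for behaviour.

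Section 5.2.1.1, added 7/30/2025, reports that the first 55 participants were counselled on U=U and coached on the knowledge questions whatever their arm. It concludes that "our analyses of the post-test knowledge and attitudes questions must omit these 55 participants", and that "recruitment was separated into wave 1 (n=55) and wave 2 (n=80"). It also says: "These changes are indicated in the relevant places below in this protocol". Section 5.2.3.2 has one such note ("Implementation note: Arm C participants were reallocated to Arms A and B"), and others stand in 5.2.3.4, 5.2.4 and 5.2.5.4. Section 5.2.8 has none.

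On the baseline, section 4.1.3 says of 363 Gauteng university students that "respondents perceived ART to reduce infection risk by 17" per cent. Section 5.2.8 says of Gauteng university students, also n=363, that they "perceived virally-suppressive ART reduced transmission risk by an average of 20% (s.d. 25" per cent).

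**The concern.** The stated power and the stated analysis set no longer agree. A reader of 5.2.8 would assume 90 analysable participants. A reader who combines it with the statement in 5.2.1.1 that Arm C's places were moved into Arms A and B to gain power could even infer that power for knowledge rose: all 135, split 67/68, would give 99.6%. For this outcome the sample in fact fell below the planned 90.

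The 17% and 20% figures share a population, a sample size and, apparently, a construct, and no explanation is offered. The baseline matters because the target is worded both as a doubling and as 20% to 40%. These are the same target only if the baseline is 20%.

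**Working it through.** **Inputs from the documents.** Difference 20 points (20% to 40%), SD 25 and 45 per arm (5.2.8); 135 enrolled, 55 omitted from knowledge and attitudes (5.2.1.1); 1:1 randomisation (5.2.3.1); alternative baseline 17% (4.1.3).

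**Assumptions.** Two-sided 5%, and the arm split within wave 2; the documents give neither. SD 25 is stated only alongside the 20% mean, and is carried over to the 17% scenarios.

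**Formulas.** SE = 25 × √(1/n₁ + 1/n₂). Normal-approximation power = Φ(difference/SE − 1.96). The t-test figures use the noncentral t with n₁ + n₂ − 2 degrees of freedom and noncentrality difference/SE.

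**Reproducing the plan's figure.** At 45/45, SE = 25 × √(2/45) = 5.270 and 20/5.270 = 3.795. Power is Φ(1.835) = 96.7% (t-test 96.4%). The stated 97% reproduces. A one-sided 5% test would give 98.4% (t-test 98.3%), so two-sided is the closer match.

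**Current analysis set.** 135 − 55 = 80. At 40/40, SE = 25 × √(2/40) = 5.590 and 20/5.590 = 3.578. Power is Φ(1.618) = 94.7% (t-test 94.2%).

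| Wave 2 split (20% to 40%, SD 25) | Normal | t-test |
|---|---|---|
| 40/40 | 94.7% | 94.2% |
| 35/45 | 94.4% | 93.9% |
| 30/50 | 93.4% | 92.8% |
| 25/55 | 91.3% | 90.6% |

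**Precision.** The 95% CI half-width for the difference (t quantile × SE) goes from 10.5 points at 45/45 to 11.1 at 40/40. The difference detectable with 80% power (t-test) goes from 14.9 to 15.9 points.

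**Baseline 17%, at 40/40 and SD 25.**

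| Target | Difference | Normal | t-test |
|---|---|---|---|
| Doubling, 17% to 34% | 17 | 86.0% | 85.2% |
| Fixed, 17% to 40% | 23 | 98.4% | 98.2% |

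The baseline conflict therefore has no fixed direction: power falls under one reading of the target and rises under the other.

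**Sensitivity to SD.** At 40/40 (t-test), power drops to 80% at an SD of 31.5 for 20% to 40%, 26.8 for 17% to 34%, and 36.3 for 17% to 40%.

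**The case against.** The best reply is that nothing has been miscalculated or hidden. A power section is a prospective justification; 5.2.8 states its own basis of 45 and 45, and 5.2.1.1, which comes earlier, openly gives the exclusion and n=80. The loss is two to three points, and the estimate with its confidence interval will show the precision achieved better than any restated power. The 94% also comes from an unadjusted two-sample comparison, whereas 5.2.6 plans regression with robust standard errors adjusted for clinic and counselling type. Section 5.2.6 has no note either, so singling out 5.2.8 is selective. Finally, 17% and 20% may be different summaries of the same survey, or a rounded planning value, and within 5.2.8 the target is self-consistent.

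Much of this stands. The 97% is not an arithmetic error, the effect is small, and 94% is a planning approximation on the same footing as the plan's own 97%, not the power of the adjusted model. The two baselines may indeed be different measures. The mismatch remains, however: the protocol says its changes are marked where they apply, and the only power statement, for the outcome most affected by the exclusion, is not marked. The lack of a note in 5.2.6 does not excuse its absence in 5.2.8. Nor do the documents say why the baselines differ.

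**Conclusion.** The point holds. Section 5.2.8 describes 90 participants and 97% power; the plan as it now stands gives 80 and about 94%, assuming two-sided 5%, SD 25 and roughly equal arms. Power for 20% to 40% stays above 90% for splits as uneven as 25/55. The 17% versus 20% conflict is a separate inconsistency. With a 17% baseline and 40 per arm, power could be as low as about 85% or as high as about 98%, depending on how the target is read. Every scenario tabulated here at SD 25 stays above 80%. The doubling from 17% has the least margin, reaching 80% at an SD of 26.8. With recruitment complete, no design decision turns on this.

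**What to change.** Keep the 45/45 sentence in 5.2.8 as the planning figure and add a dated implementation note that:

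- states that the post-test knowledge and attitudes analyses use wave 2 only (n=80), with the actual Arm A and Arm B counts;
- gives alpha and sidedness, and the restated power: about 94% for 20% to 40% if the arms are near 40 each, at two-sided 5% and SD 25.

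Check the 17% in 4.1.3 and the 20% in 5.2.8 against the source survey. Either reconcile them or say that they are different measures. State whether the target is a doubling or a fixed 40%. If the baseline proves to be 17%, report the matching power (85–86% for 17% to 34%, about 98% for 17% to 40%, both at 40 per arm and SD 25).

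The cost is one note and one reconciled figure, with a slightly less favourable stated power. Only the wave 2 arm counts and the source survey are needed; no new data have to be collected.

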7.1. Information sheet and consent form

Upon completion of eligibility screening, the study interviewer will complete the informed consent process. The interviewer will use the information sheet to describe the study in detail, answer any questions that participants might have, as well as work through a standardized Question and Answer information supplement. Once all questions have been answered, the consent process will be documented on the signed consent form. The information sheet and consent form for our study describes the nature goals and procedures of the study. The consent form will be administered by a trained study staff member in English, Sotho, Zulu and Xhosa(depending on the participant's preference). The information sheet will explain that if participants choose to be in the study they will be asked to complete a questionnaire. Participants will be assured that data collected for our study will be kept strictly confidential. They will be told that participation in the study is completely voluntary.

This documentation will be left with participants and will include the contact details of the Principal Investigator, the Project Director and the Chair of the Wits HREC, should they wish to contact the study team or lodge a complaint. If participants are illiterate, they will be asked to bring in another person who can read who will witness the consent process. The third party will sign the consent form, and the illiterate participant will mark the consent form.

7.2. Potential Risks

We believe that our study poses no physical risks to subjects beyond those routinely encountered. It may, however, pose risks associated with breach of confidentiality and disclosure of HIV status.

Loss to HIV care

The proposed research aims to increase uptake of HIV treatment and to reduce losses in the HIV care cascade. To do so, we will provide key information on the prevention benefits of ART through an educational video intervention. Although we anticipate that providing information on U=U will increase uptake and adherence to ART, there is a risk, however small, that patients who receive this intervention will start and stay on ART at a lower rate.

Breach of confidentiality

A potential risk of the study concerns the confidentiality of data about HIV status and treatment program enrollment. A high level of stigmatization continues to inhibit the disclosure of HIV status in the study population. Data collected in surveys or clinic records could be disclosed and reveal a person's HIV status. There is always the possibility of a breach of confidentiality when conducting research. While this is acknowledged, there is very low likelihood because of the precautions that will be taken to protect confidentiality.

Unintended behavioral consequences

There is a risk that providing individuals with information on treatment-as-prevention will lead to risk compensation behaviors and elevated rates of unprotected sex as individuals (accurately) perceive lower risks of HIV transmission from unprotected sex with partners on ART. Such behavior could lead to increased exposure to – and transmission of – other sexually transmitted infections, and to unintended transmission of HIV if people with HIV do not adhere to ART and are not virally suppressed. Clear and accurate information on these risks will be provided. These risks will be mitigated by providing carefully crafted counseling messages as described below. While these are real risks, the risks of NOT providing information on ART as a technology to reduce HIV transmission risk are very large, given the large share of HIV-infected people not yet on ARVs who continue to have unprotected sex (as discussed in the Research Strategy section). Data on self-reported ART adherence and sexual behavior will be collected at baseline and 6-months follow-up to assess potential adverse consequences.

Emotional distress

The study population for this study will be patients who receiving HIV counseling as part of standard of care. These patients include those who have been newly diagnosed with HIV as well as patients who are receiving adherence counseling. Though unlikely, it is possible that information presented on U=U may cause some emotional distress for some potential subjects. The intervention will be implemented in coordination with HIV counselors at public sector

clinics. These counselors are trained to identify and support patients in emotional distress. Patients who counselors identify as being in emotional distress will not be referred to the study. Further, study participants who experience emotional distress during the survey will be referred to the HIV counselors on site for support.

